Sensitization in kidney transplant candidates. Alloantibodies (anti-HLA antibodies) arise through previous transplants, blood transfusions, and pregnancy. Currently, 39% of patients on the active kidney transplant waitlist are sensitized, evidenced by a Panel Reactive Antibody (PRA) $\geq 1\%$ (33). Of these, nearly 15,000 are highly sensitized, which means that they have a PRA $\geq 80\%$ (33). Transplant rates vary by PRA, ranging from 143.0 per 100 active waitlist years for candidates with a PRA of less than 1% to only 6.9 for those with a PRA of 98% or higher (33). Median waiting time for kidney transplantation in highly sensitized patients approaches 12 years, which is more than 3 times than for non-sensitized patients (33). As a result, a significant number of highly sensitized patients die before receiving a transplant, outlining the critical importance of desensitization strategies.

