2.2 Secondary Objectives

Specific Aim 2. Identify immune indices which predict the course of disease and/or response to treatment in highly sensitized patients. Mechanistic studies will use bone marrow and blood obtained from subjects in Aim 1 to determine the effect of treatment on immune regulation and reconstitution after therapy. Since the bone marrow microenvironment produces BAFF/APRIL and supports plasma cell maturation, we will determine the effect of therapy on the generation of BAFF/APRIL by bone marrow mesenchymal stem cells and the survival of bone marrow-derived plasma cells after desensitization. We specifically propose to:

- Identify if bone marrow plasma cells, IgG subsets, and circulating BAFF/APRIL predict outcomes.
- Determine if treatment is effective in downregulating circulating BAFF/APRIL and anti-HLA, endothelin-1 type A receptor (ETAR), angiotensin type 1 receptor (AT1R), and complement fixing C1q antibodies.
- Identify immunological indices which predict treatment toxicity and responders vs. non-responders.

In summary, sensitization is a significant clinical and immunological problem in kidney transplantation. In a unique effort involving the University of Wisconsin's Divisions of Nephrology, Transplantation, and Hematology-Oncology (clinical core), The University of Michigan (Plasma cell core), and The Terasaki Foundation Laboratory (DSA core), coordinated by the UW Office of Clinical Trials, an experienced clinical research organization, we propose the planning of a pilot phase II safety and efficacy trial of ixazomib for desensitization of highly sensitized kidney transplant candidates. We further outline mechanistic studies to determine the pathogenesis of alloantibody generation and define novel biomarkers and surrogate endpoints for a future Clinical Trial Implementation grant (NIAID PAR-13-149). The results are expected to have a positive impact as proposed studies are crucial steps towards developing improved therapies and monitoring options to reduce the long-term impact of sensitization.

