4.2 Number of Patients

A total of 10 patients will be enrolled in this pilot clinical trial. We currently have more than 40 patients that qualify for the study based on the inclusion criteria described below. A patient will be considered enrolled after the first day of ixazomib treatment.

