5.1 Inclusion Criteria

Each patient must meet all of the following inclusion criteria to be enrolled in the study:

1. Male or female patients 18-70 years of age.
2. Able to provide informed consent.
3. Female patients who are postmenopausal for at least 1 year before the screening visit, or are surgically sterile, or If they are of childbearing potential, agree to practice 2 effective methods of contraception, at the same time, from the time of signing the informed consent

form through 30 days after the last dose of study drug, OR agree to practice true abstinence when this is in line with the preferred and usual lifestyle of the subject. (Periodic abstinence [eg, calendar, ovulation, symptothermal, post-ovulation methods] and withdrawal are not acceptable methods of contraception.)

4. Male patients, even if surgically sterilized (ie, status post-vasectomy), must agree to one of the following: Agree to practice effective barrier contraception during the entire study treatment period and through 30 days after the last dose of study drug, or Agree to practice true abstinence when this is in line with the preferred and usual lifestyle of the subject. (Periodic abstinence (eg, calendar, ovulation, symptothermal, post-ovulation methods] and withdrawal are not acceptable methods of contraception.)
5. Patients must be highly sensitized with a cPRA $\geq 80\%$
6. Be active on the waitlist for kidney transplantation > 24 months to confirm their inability to receive a deceased donor transplant because of their sensitization status.
7. Patients must meet the following clinical laboratory criteria:
 - Absolute neutrophil count (ANC) $\geq 1,000/\text{mm}^3$ and platelet count $\geq 75,000/\text{mm}^3$. Platelet transfusions to help patients meet eligibility criteria are not allowed within 3 days before study enrollment.
 - Hemoglobin higher than 6 g/dL
 - Total bilirubin $\leq 1.5 \times$ the upper limit of the normal range (ULN).
 - Alanine aminotransferase (ALT) and aspartate aminotransferase (AST) $\leq 3 \times$ ULN.

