6.12 Termination of Treatment and/or Study Participation

Patients will be informed that they have the right to withdraw from the study at any time for any reason, without prejudice to their medical care. The investigator also has the right to withdraw patients from the study for any of the following reasons:

- If study drug is discontinued due to AE
- Protocol violation
- Lost to follow-up
- Study terminated
- Non-compliance as defined above in section 6.10

Patients who are withdrawn from the study will not be replaced. The primary reason for patient's withdrawal from the study should be recorded in the source documents and CRF. Subjects will complete an early termination visit.

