7. STATISTICAL AND QUANTITATIVE ANALYSES

7.1 Statistical Methods

More than 50% of patients with CDC T cell crossmatch titers $\geq 1:8$ and/or cPRA $> 80\%$ fail to respond to desensitization (5, 8). In this pilot exploratory, proof of concept, open-label, single-center phase II clinical trial, we hypothesize that our study will have a higher rate of transplantation. [name], PhD, epidemiologist and biostatistician in the division of nephrology, will perform the statistical analyses. *Primary* efficacy (decline in cPRA $> 20\%$) and safety (discontinuation of therapy due to adverse events) endpoint will be analyzed using the exact binomial test. The *secondary* endpoint (time to transplantation) will be assessed using Kaplan-Meier analyses and log rank tests. Baseline characteristics will be compared between participants with and without the primary end point using the 2-sample t test for continuous variables and the Fisher's exact test for categorical variables. Relationships between serum BAFF/APRIL, antibodies, and baseline cPRA will be assessed using the Pearson correlation coefficient. The influence of serum BAFF/APRIL, antibodies, and bone marrow plasma cells on end points of interest will be investigated using Kaplan-Meier curves and Cox proportional-hazards models.

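### Cox models relating biomarkers to endpoints in 10 patients give unreliable inference at the one to three events the protocol's own figures suggest

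*Combined protocol and SAP*

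**What the plan says.** Section 2.2 sets the aim: "Identify immune indices which predict the course of disease and/or response to treatment in highly sensitized patients". For the relation of BAFF/APRIL, antibodies and marrow plasma cells to the endpoints, Section 7.1 states that it "will be investigated using Kaplan-Meier curves and Cox proportional-hazards models". Section 3.3, under tertiary and exploratory endpoints, repeats Kaplan-Meier and Cox for BAFF/APRIL. Before that step it asks whether baseline BAFF/APRIL was higher in patients who did not reach an endpoint, without naming a test. It also aims to show that BAFF or APRIL independently predicts sensitization markers such as cPRA and DSA, and for that question it allows nonparametric as well as parametric methods.

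For markers against sensitization at entry, Section 7.1 says: "Relationships between serum BAFF/APRIL, antibodies, and baseline cPRA will be assessed using the Pearson correlation coefficient".

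On numbers, Section 4.2 says "A total of 10 patients will be enrolled in this pilot clinical trial" and Section 6.12 adds "Patients who are withdrawn from the study will not be replaced". No event count, significance level, choice of Cox test, small-sample correction or multiplicity rule is given for these analyses.

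**The concern.** A Cox model draws its information from events, not patients. With 10 patients and a handful of events, the partial likelihood may have no finite maximum, and the large-sample tests lose their nominal error rates in different directions. Because the plan names no test, the same data could yield a significant p-value from one standard output line and nothing from another. Section 2.2 says that the mechanistic work should define biomarkers and surrogate endpoints for a later trial grant, so an empty or falsely significant hazard ratio could steer that choice.

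**Working it through.** **Check on the plan's own figures (Section 7.1.1).** Exact 95% limits for 3/10 are 6.67% to 65.25% (plan: 6.7% to 65.2%). P(at least one success at a true rate of 0.2) = 1 - 0.8^10 = 89.3% (plan: above 80%). Both reproduce, but they concern the primary endpoint only.

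**Events to expect among 10 patients.**
- Transplantation: Section 1.9 gives "only 6.9 for those with a PRA of 98% or higher", per 100 active waitlist years. One-year risk = 1 - exp(-0.069) = 6.7%, so 0.67 events are expected. P(0) = 0.933^10 = 50%, P(0 or 1) = 86%, P(0 to 3) = 99.7%.
- cPRA response: expected events are 2.0 at 20% (power example, Section 7.1.1), 2.6 at 26.3% (an earlier bortezomib experience, Section 1.1.1) and 3.0 at 30% (the 3/10 example). P(0 to 3) is 88%, 74% and 65%. At 50% it is 17%.

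**Infinite estimates.** With one covariate and nobody censored before the last event, the estimate is infinite if each event patient has the most extreme marker value in the risk set, always in the same direction. Under no effect:
- 1 event: 2/10 = 20%
- 2 events: 2/(10 × 9) = 2.2%
- 3 events: 2/(10 × 9 × 8) = 0.3%

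Simulations agree (about 18-20% with 1 event). With 1 event, an infinite fit has a likelihood-ratio statistic of 2 ln 10 = 4.61, above the 5% cut-off of 3.84. Each such fit therefore counts as significant, which explains an error rate near 20%.

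**Simulated rejection rates under no effect.** Settings: n = 10, one covariate, two-sided 0.05 (assumed), normal or log-normal marker (assumed), 20,000 runs per setting.

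| Events | Likelihood ratio | Wald | Score | Exact rank-sum |
|---|---|---|---|---|
| 1 | 19-20% | 0% | 4-8% | 0% |
| 2 | 8.5-9.1% | 0% | 5-7% | 4.5% |
| 3 | 7.2-8.3% | 0.2-0.4% | 5.5-7% | 3.3-3.4% |
| 5 | about 7% | 2-3% | 6-7% | 3.1% |

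**Power.** The hazard ratio per SD needed for 80% power is exp((1.96 + 0.84)/√events): 16.5, 7.3, 5.0 and 3.5 for 1, 2, 3 and 5 events. At a true hazard ratio of 4 per SD, simulated power with 1, 2 and 3 events is:
- Wald: 0%, 0%, 2-7%
- likelihood ratio: 41-42%, 38-39%, 47-49% (with the inflated error above)
- score: 12-35%, 29-47%, 42-58%
- exact rank-sum: 0%, 24%, 28-29%

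**Limit of exact tests.** The smallest two-sided rank-sum p-value is 2/C(10, k): 2/10 = 0.20, 2/45 = 0.044 and 2/120 = 0.017 for 1, 2 and 3 events. With 0 events there is no test.

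**Pearson at n = 10.** Simulated type I error is 4.0-5.9%. Power against exact Spearman:
- Correlation 0.7, uniform cPRA and normal marker: 66% against 56%.
- Correlation 0.7, both normal: 68% against 56%.
- Correlation +0.7, skewed marker and cPRA piled up near 100: 10-20% against 55-56%.
- Correlation -0.7, both skewed: 53-57% against 55-56%.

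**The case against.** **Status.** The trial is labelled a pilot and exploratory, Section 3.3 files these analyses as tertiary, and no decision rule hangs on them. This limits the importance of the point. It does not make the planned hazard ratios or p-values readable.

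**The score test.** It stays near nominal and, in most settings run, has more power than the rank-sum test. That is correct, so the inflated error belongs to the likelihood-ratio test and not to every Cox analysis. But the plan does not select the score test, and a near-nominal p-value does not repair an infinite or extreme estimate.

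**Partly covered already.** Section 3.3 starts with a group comparison, and Section 7.1 plans a two-sample t test of baseline characteristics by primary endpoint status. With 2 or 3 responders that t test held its error rate (3.1-5.4% across settings) and had more power than the rank-sum test in every setting run. The fix therefore extends something the plan half contains, and is not a gain in power.

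**Readings that go too far.** A reader might infer that 0 to 3 events is a planned figure. It is not: it is near certain for transplantation at the background rate, 65-74% likely for cPRA response at 26-30%, and unlikely at 50%. The 6.9 figure is for PRA 98% or higher, whereas entry requires cPRA of at least 80%. A reader might also infer that Pearson is an error here. Its error rate is acceptable, its power deficit depends on distributions the documents do not give, ranks do not undo the restriction of cPRA to 80-100%, and Section 3.3 already permits nonparametric methods for that question.

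**Conclusion.** The point holds for the Cox models. At 1 to 3 events the likelihood-ratio error is about 19%, 8.5% and 7-8%, the Wald test is almost inert, and with 1 event about one estimate in five is infinite. At 5 events the distortion is milder (about 7% and 2-3%), but only hazard ratios of about 3.5 per SD are detectable with 80% power. This rests on event counts inferred from the protocol's cited rates, an assumed two-sided 0.05, assumed marker distributions, and no censoring before the last event.

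The planned Pearson correlations do not need correcting. A reader might also expect exact tests to rescue the analysis. They cannot at 0 or 1 event, which is the likeliest outcome for transplantation at the background rate. Their merit is that they show that limit openly. The point is worth making because it is cheap to act on; it does not threaten the primary analysis.

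**What to change.** In Sections 3.3 and 7.1:
- Replace the Cox models with an exact permutation or rank comparison of baseline biomarkers between patients with and without each endpoint, with every patient's value plotted.
- State that with 0 or 1 event the result is descriptive only, and give the smallest attainable rank-sum p-values (0.20 with 1 event, 0.044 with 2).
- In Section 3.3, replace the claim of independent prediction with one of association. Independence would need multivariable models, which 10 patients support even less.

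Optional: report Spearman with an exact p-value beside Pearson for markers against baseline cPRA, as a robustness measure. It costs about 10-12 points of power if the data are near-normal; the large gain appears when marker and cPRA are both skewed and positively related.

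Cost: wording only, with no new data. No hazard ratio is reported, the group comparison ignores event timing, and power remains low.

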7.1.1 Determination of Sample Size

The primary outcome will be considered as a dichotomous outcome (decline in cPRA of $>20\%$ or not). We will test the hypothesis that the success rate (i.e., the % that have a decline in cPRA $>20\%$) is 0% using the exact binomial test (Figure 2a) (5). The figure shows the lower and upper 95% confidence limits resulting from any observed success rate. For example, if we observe success in 3/10 (30%), the resulting 95% confidence interval (CI) is (6.7%, 65.2%). Any observed success demonstrates that the success rate of the proposed treatment is >0 . Figure 2b represents the power curve, that is, the probability of observing any success, given different values of true success rate. For example, we would have $> 80\%$ chance of observing at least one success if the true success rate is > 0.2 .

Figure 2a. Sample Size Analysis

[figure not shown]
[figure not shown]

Figure 2b. Power curve

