The two approaches for helping highly sensitized patients are: 1) To increase the chance of finding a crossmatch negative donor, or 2) To remove the pre-existing antibodies using desensitization protocols (7-11). Emerging evidence suggests that strategies to improve transplant rates in highly sensitized patients enhance survival rates and the quality of life, while reducing costs compared to chronic dialysis (12, 13). Current desensitization protocols combine Rituximab (anti-CD20 monoclonal antibody) to deplete B cells, and plasmapheresis plus intravenous immunoglobulins (IVIG) to block or remove preformed DSA (7-11). Since no agent previously used in transplantation has the adequate ability to inhibit mature plasma cells, there has been no effective way of reducing or preventing antibody production besides targeting B cells. Therefore, despite some success, contemporary desensitization protocols are limited by their inability to desensitize 30 to 90% of patients (5, 8, 14). For example, using a preconditioning regimen similar to the one used at our institution combining plasmapheresis, IVIG and Rituximab, the Mayo Clinic Transplant Program was unable to desensitize 15/29 patients who had an CDC crossmatch titer $\geq 1:8$ (8). Similarly, Marfo et al demonstrated that pretransplant desensitization with high dose IVIG and rituximab was not successful in sensitized kidney transplant candidates with cPRA levels higher than 90% (5). It is for this reason that we propose a pilot desensitization study targeting the cells responsible for generating alloantibodies using ixazomib (Ninlaro[®]), a second generation proteasome inhibitor, recently approved therapy for multiple myeloma.

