7.1.6 Efficacy Analysis

Primary outcome will be a decline in cPRA > 20%. Secondary outcome will be kidney transplantation within 12 months of therapy. These outcomes will be assessed using paired t-Test, Kaplan-Meier methods and log rank tests, where appropriate. In addition, we will analyze the change in HLA antibody strength by comparing the MFI values pre and post therapy.

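### The primary efficacy test uses a null of exactly 0%, so it only restates whether any of 10 patients succeeded; section 7.1.6 then drops that test and adds a paired t-test that does not fit the yes/no outcome

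*Combined protocol and SAP*

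**What the plan says.** The trial is a single-arm pilot: "A total of 10 patients will be enrolled in this pilot clinical trial" (section 4.2). Section 7.1.1 treats the primary efficacy outcome as dichotomous (cPRA decline >20%, yes or no), sets the hypothesised success rate at 0%, and applies the exact binomial test. It concludes: "Any observed success demonstrates that the success rate of the proposed treatment is >0". It gives exact 95% limits, with 3/10 as the worked example, and describes the power curve in Figure 2b openly: "that is, the probability of observing any success" at various true rates. Its example is a better than 80% chance when the true rate exceeds 0.2.

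Section 7.1 agrees on the method. The primary efficacy and safety "endpoint will be analyzed using the exact binomial test", and the next sentence gives Kaplan-Meier and log rank tests to the secondary endpoint, time to transplantation.

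Section 7.1.6, the efficacy analysis section, restates the primary and secondary outcomes together and continues: "These outcomes will be assessed using paired t-Test, Kaplan-Meier methods and log rank tests, where appropriate". The binomial test does not appear there.

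**The concern.** There are two separate problems.

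First, a null of exactly 0% makes the test a relabelling of the count. One responder in 10 becomes a formal rejection and can be reported as a positive primary result, although the interval around it runs from almost nothing to nearly one half. The curve presented as power has the same property: it is power to see one event, not power against any reference rate that would matter to a reader.

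Second, the section where an analyst would look for the efficacy method names a different set of methods. The paired t-test analyses a mean change. If it stays unassigned, the choice between a responder rate and a mean cPRA change can be made after the data are seen.

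**Working it through.** **Inputs.** n = 10 (section 4.2); null rate p0 = 0 and success = cPRA decline >20% (section 7.1.1). The plan states no alpha or sidedness for the test, only 95% limits.

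**The plan's own figures.** The Clopper-Pearson 95% CI for 3/10 is 6.67% to 65.25%, matching the stated 6.7% to 65.2%. The chance of at least one success at a true rate of 0.20 is 1 − (1 − 0.20)^10 = 1 − 0.107 = 0.893, consistent with the stated >80%. The arithmetic in section 7.1.1 is correct.

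**Behaviour of the test.** If p0 = 0, then P(X = 0) = 1 and P(X ≥ 1) = 0. The p-value is therefore 1 at 0/10 and 0 at every other count, one- or two-sided, and the rule is at least one success in 10 whatever alpha is chosen. The exact interval carries the same decision, because its lower limit is above zero exactly when the count is, and it carries more besides:

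| Successes | Exact 95% CI | p-value against 0% |
|---|---|---|
| 0/10 | 0% to 30.8% | 1 |
| 1/10 | 0.25% to 44.5% | 0 |
| 3/10 | 6.7% to 65.2% | 0 |

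**Where the curve reaches 80%.** Solving 1 − (1 − p)^10 = 0.80 gives p = 1 − 0.2^(1/10) = 0.149.

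**Is 0% a useful benchmark?** Section 1.1.1 reports 26.3% responders in one bortezomib experience, and says contemporary protocols fail to desensitize 30 to 90% of patients, so 10 to 70% are desensitized. Section 7.1 says more than 50% fail to respond, which is not all of them. These are treated rates, and their response definitions may differ from a cPRA decline >20%. They still show that a rate above zero does not distinguish this regimen from others.

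**What a non-zero reference would require.** Illustration only, at an assumed one-sided alpha of 0.05, with reference rates taken from those figures:

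| Reference rate | Successes needed | Exact alpha | Power at true rate 30% / 40% / 60% |
|---|---|---|---|
| 10% | ≥4/10 | 0.013 | 35% / 62% / 95% |
| 26.3% | ≥6/10 | 0.025 | 5% / 17% / 63% |

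One success in 10 rejects neither.

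**Methods set side by side.** Primary efficacy: exact binomial in 7.1 and 7.1.1, not mentioned in 7.1.6. Kaplan-Meier and log rank: assigned to time to transplantation in 7.1, listed for both outcomes in 7.1.6. Paired t-test: listed only in 7.1.6, with no outcome assigned. It cannot be applied to the dichotomous outcome of 7.1.1; it would fit continuous cPRA change. A log rank test compares groups; this trial has one arm, and no section names the groups for this test.

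**The case against.** The best defence is that this is a declared pilot and proof-of-concept study. The quoted sentence is true, the meaning of the curve is disclosed, exact limits accompany the test, and no alpha or go/no-go rule is tied to it. All of that stands. It limits the seriousness of the point, but it also shows that the test can be removed without losing information.

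Four stronger readings are tempting, and the documents do not support them.

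- A reader might infer that the trial has an inflated false-positive rate. At assumed true rates of 1%, 5% and 10%, the 0% null is rejected with probability 1 − (1 − p)^10 = 9.6%, 40.1% and 65.1%. These are not type I errors of the stated test: if the true rate is not zero, rejecting zero is correct. Nor do the documents give a background rate of such declines.
- A reader might infer that no primary efficacy method is named. Sections 7.1 and 7.1.1 both name the exact binomial test. Read with them, the qualifier in 7.1.6 can send Kaplan-Meier and log rank to transplantation. What remains is the omission of the binomial test from 7.1.6, the unassigned paired t-test, and a log rank test without groups.
- A reader might infer that the source cited for 0% covers the wrong population, because section 1.1.1 describes it at cPRA above 90% and entry is at 80% or more. Section 7.1 cites the same source, with another, for cPRA above 80%. The source is not available here, so the inference is unsafe.
- A reader might infer that reporting an interval would isolate the drug effect. It would not. Separating drug effect from background change is a limit of the single arm, whichever summary is used.

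**Conclusion.** The point holds and should be fixed, as a matter of what the analysis claims rather than of calculation. The primary test is uninformative by construction: its outcome is fixed by whether the count is zero, and it adds nothing to the exact CI. The better than 80% statement is right for at least one success (89.3% at 0.20) but is not power against a meaningful rate. Section 7.1.6 is inconsistent with 7.1 and 7.1.1, and the practical exposure is a later choice between a responder rate and a mean change.

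The test result and the intervals rest only on n = 10 and a 0% null. The view that 0% is a weak benchmark rests on the protocol's own figures for other regimens, subject to the caveat about response definitions. The cut-offs for non-zero reference rates also assume one-sided alpha 0.05.

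**What to change.** 1. In sections 7.1, 7.1.1 and 7.1.6, make the primary efficacy result the observed proportion with a cPRA decline >20% and its exact (Clopper-Pearson) 95% CI. Delete the test against 0% and the sentence on any observed success. In 7.1 the efficacy and safety endpoints share one sentence, so separate them.
2. State the denominator as all enrolled patients, with enrolment as defined in section 4.2, and say how patients without a post-baseline cPRA count, for example as non-successes. This is needed because section 7.1.3 defines only a safety population, withdrawn patients are not replaced (6.12), and 7.1.4 allows last observation carried forward without saying where it applies.
3. In 7.1.6, label the paired t-test supportive and restrict it to continuous cPRA change. Keep Kaplan-Meier for time to transplantation. Remove log rank from 7.1 and 7.1.6 unless its comparison groups are stated.
4. Retitle Figure 2b as the probability of at least one success.
5. Optional: if a formal test is wanted, state and justify a non-zero reference rate, starting from the protocol's own figures, with alpha and an exact cut-off, and redraw the curve.

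The cost is wording and one figure title; endpoint, patients, visits and samples are unchanged. The protocol loses its formal primary test and its power statement. If a test is kept under item 5, power with 10 patients will be low for moderate effects, as the illustration shows. CI width does not change, and the single-arm limit remains.
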